dose/frequency, type of maintenance medication use (e.g. reduction/discontinuation in opiate use) also with real time, daily diaries. We will also examine whether or not MM patients experience loss of control over intake of marijuana or other substances. We will use measures such as development of tolerance, escalation of use, marijuana caving, and assess experience of reinforcing effects (e.g. euphoria or 'high'), and withdrawal among those who choose to stop using marijuana.

Any changes throughout 12 months in perception of disease symptomatology or in use of maintenance medication will be compared to the waitlist control group.

Aim 2: To assess neurocognitive and psychiatric effects of MM. We expect that neurocognitive outcomes, such as working memory, attention, executive function, anhedonia, amotivation, and decision-making, (when not acutely intoxicated) may be worsened with MM use. Outcomes may be worse in those who use more frequently/heavily (as measured by quantitative THC screens and dosing dairies).

Aim 3: In a subset of patients, assess how MM effects neurocircuitry of prefrontal function. We will use functional MRI tasks to assess working memory, inhibitory control, sustained attention, and risk/reward task performance and brain activation patterns. We expect that individuals who use MM may experience changes from baseline in neurocircuitry involved in memory, attention, inhibitory control and reward.

Aim 4: To assess how medical marijuana patients compare to healthy controls in structural and functional brain imaging measures. We will use functional MRI tasks to assess memory, inhibitory control, sustained attention, and risk/reward task performance and brain activation patterns. We expect that individuals who use MM to show alterations in task-related brain activity.

III. PARTICIPANT SELECTION

Medical Marijuana Participants

Inclusion Criteria:

1. Men and women aged 18-65 years, inclusive;
2. Competent and willing to provide written informed consent;
3. Desire to use medical marijuana for self-reported pain, sleep, or affective (mood and/or anxiety including PTSD) symptoms.
4. Not in possession of a medical marijuana card, but expressing intent to get one.
5. Able to communicate in English language.

Exclusion Criteria:

1. Current daily marijuana use (prior to enrollment)

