4. Pregnancy (if the subject cannot rule out the possibility of pregnancy, a pregnancy test will be conducted prior to the study)
5. In the opinion of the investigator, not able to safely participate in this study.

IV. RECRUITMENT METHODS

Participants will be recruited by study staff at the MGH Center for Addiction Medicine through advertising by email, web and bulletin board announcements posted within the local site network community. We will place a Partners HRC approved research study advertisement on relevant websites and in relevant print publications, as well as on the MBTA and on radio advertisements. We will also recruit from local clinics.

In accordance with NIH guidelines, efforts will be made to attain a mix of study participants, in terms of gender and racial/ethnic representation that is reflective of the population of the greater metropolitan area where the recruitment is taking place. For example, for the metropolitan Boston area we will attempt to recruit; 63% white, 26% African American and 11% other races. We anticipate that half of our participants will be male and half female and that we will have representation from Asian American, African American and Hispanic minority groups in our final cohort that is representative of that reported in census data for Greater Boston.

V. STUDY PROCEDURES

Healthy Control Participants

Screening: Participants who have expressed interest in participating in the study will undergo a brief phone screen to assess eligibility. We plan to phone screen about 100 participants. If they are eligible according to the phone screen, they will be scheduled for an in-person study visit. At this visit, a consent form will be reviewed with the study doctor. If participants are determined eligible at the end of this visit, they will then be scheduled for the MRI scan.

Study Design:

Visit I: Healthy Control Screen

Visit I of this study will take place outside of the scanner only. Participants will be recruited and scheduled for a behavioral session. In this session, we will test participants on a computer in order to optimize the parameters of the task.

Visit II. Healthy Control Imaging Procedure

In Visit II, participants who have met all inclusion criteria and none of the exclusion criteria will be scheduled for an MRI scan. Each scan session will last up to two hours during which structural and/or functional images will be collected.

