Screening: Participants who have expressed interest in participating in the study will undergo a brief phone screen to assess eligibility. We plan to phone screen about 2000 participants. If they are eligible according to the phone screen, they will be scheduled for an in-person (or teleconference) study visit. At this visit, a consent form will be reviewed with the study staff. Participants who give permission to receive text messages from the study staff will receive appointment reminders via text two days before upcoming appointments. In addition, subjects will be instructed on how to use our phone app for tracking their medical marijuana use, they will fill out some questionnaires and also do a urine drug and if applicable, a pregnancy test. Also at this visit, participants will be randomized to either the active study group or the waitlist control group. We plan to randomize 200 participants to each group.

Study Design: The active study group will be asked to call the study staff once they receive their MM cards. A staff member will follow up via phone with participants who do not contact study staff within approximately two weeks after the screening visit. Staff will contact participants again after approximately four weeks and six weeks to check in on the status of the medical marijuana card application. If after six weeks, a participant still has not made any progress on the application for a

medical marijuana card (i.e., made an appointment with a doctor who recommends medical marijuana), the participant will be discontinued from the study and a three-month follow-up visit will be scheduled.

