When participants in the active study group receive their medical marijuana card, they will be scheduled for a baseline assessment in which they will undergo cognitive testing, interviews, questionnaires, and possibly an MRI scan (see Measures below). In contrast, participants in the waitlist control group will be scheduled for the baseline visit approximately 3-4 weeks following the screening visit. All participants will then be scheduled for repeat assessments at approximately 2 weeks, 1 month, 3 months, 6 months and 1 year after the baseline visit. All participants will receive monthly check in phone calls from a research coordinator at approximately 2, 4, 5, 7-11 months past baseline in order to update study staff on medication changes, recent substance use, and overall physical and mental health. Participants will also be asked to complete a 2-year follow-up phone call, which is identical to previous check in calls, with the addition of the CGI and CUD checklist. If participants are in the active study group, we will ask that they not use MM on the day of testing (though they can use it after testing on that day). These visits will take approximately 3 hours to complete.

In consultation with their prescribing physician, participants in the waitlist control group will be asked to wait to start using MM until they have completed Visit 5 (Three Months). During those 3 months, they will be assessed at the same time points as those in the active MM group (see study schema). After the 3-month waitlist period, the waitlist control group will have the option to start using MM. If this group fails to adhere to the waitlist control, they will be kept in the study and will be asked to complete the same assessment schedule as those initially assigned to the active study group. All participants will be assessed after 1 year.

Measure	Instrument	Visit 1	Visit 2	Visit 3	Visit 4	Visit 5	Visit 6	Visit 7
		Screen	Baseline	Two Weeks	One Month	Three Months	Six Months	One Year
General Medical/Psychiatric Health								
Medical History/ CON MEDS		x	x	x	x	x	x	x
Quantitative cannabinoids			x	x	x	x	x	x
Drug Screen/pregnancy		x	x	x	x	x	x	x
Psychiatric Interview	MINI 7 + Past SUD and AUD	x						x
Suicidality and Health Risk Taking	CHRT	x	x	x	x	x	x	x
Emotional and physical Functioning	SF-12		x	x	x	x	x	x
ADHD symptoms	ASRS		x					x
Impulsivity	BIS-11		x			x	x	x
Executive function	BRIEF		x			x	x	x
Risk perceptions and behavior	DOSPERT		x			x		

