MRI Protocol (Optional): The purpose of the MRI portion of the study is to investigate possible changes in the brain from those who obtain MM cards. Therefore, only patients randomized the active MM group will be given the option to undergo a 3T MRI scanning. Participants will undergo MRI scanning at baseline and at 1 year after initiation of MM. In addition, a small group (n = 25) of non-MJ-using controls, matched on demographics, will also be scanned at baseline and after 1 year in order to allow us to assess normative change over time. Each scan session will last up to two hours during which structural and functional data will be collected. Participants will be positioned in the scanner and outfitted with audio and visual presentation and response indicator equipment. Visual images and auditory stimuli will be presented using MRI compatible presentation software and hardware. Participant responses are monitored using MRI-compatible keypads, and reaction times may be recorded for subsequent analysis of timing and accuracy of task performance.

Participants may undergo the scans noted below:

1. Structural MRI

For the structural imaging sessions T1 -weighted sequences may be acquired. Multiple anatomical imaging sequences may be run to assess specific image quality measures. The same anatomical scans will be repeated varying a limited range of pulse sequence parameters to assess their effect on the image contrast, image artifacts and signal to noise ratio. Parameters that will be varied may include the repetition time of the MR acquisition (TR), the echo time of the acquisition (TE), and the presence of pre-acquisition inversion pulses. The above parameters will also be evaluated in pulse sequences, which acquire parameters used in the reconstruction of the MR images. The software and hardware interlocks put in place by the scanner manufacturer ensure that the range of these parameters will be maintained within the FDA's non-significant risk criteria.

2. Functional Magnetic Resonance (fMRI)

The scanner is outfitted with audio and visual presentation and response indicator equipment. All tasks are programmed using presentation software that is synchronized with the video

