All phases and aspects of this project will be conducted according to the Declaration of Helsinki, and will comply with HIPAA regulations. The sponsors of this research will only have access to data on individuals that is stripped of all unique identifiers according to HIPAA guidelines.

Biostatistical Analysis

Data variables collected for study

Standardized questionnaires, assessing drug use, personality characteristics, and anxiety will be collected. Cognitive data will be collected using standardized computer programs such as the CANTAB. MRI data will also be collected.

Data will be collected and managed using REDCap (Research Electronic Data Capture) tools (Harris 2009) hosted with Partners HealthCare. REDCap data collection projects rely on a thorough study-specific data dictionary defined in an iterative self-documenting process by all members of the research team with planning assistance from Partners HealthCare Research Computing, Enterprise Research Infrastructure & Services (ERIS) group. The REDCap Survey is a powerful tool for building and managing online surveys. The research team can create and design surveys in a web browser and engage potential respondents using a variety of notification methods. Participants will complete a number of REDCap Surveys using a tablet provided to them at study visits. This platform allows access to specific surveys and participants are required to initial at the completion of each. Study staff members will initial to indicate who completed each item. Both REDCap and REDCap Survey systems provide secure, HIPAA compliant, web-based applications that are flexible enough to be used for a variety of types of research, provide an intuitive interface for users to enter data and have real time validation rules (with automated data type and range checks) at the time of entry. Online dosing diaries will be collected using Secure Survey, a web application designed to collect data from a modern user group on their mobile, tablet, or desktop devices. This platform secures not only the data transmission, but also the storage using industry standard security techniques.

Analytic Plan

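### Healthy controls have a computer session on the task before their scan and no such session is described for marijuana patients, so task exposure may differ by group in the Aim 4 task contrast

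*Combined protocol and SAP*

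**What the plan says.** **Healthy controls** (V. Study Procedures, Healthy Control Participants). The first visit is a behavioural one: "Visit I of this study will take place outside of the scanner only". Its content is given as: "In this session, we will test participants on a computer in order to optimize the parameters of the task". The scan comes later: "If participants are determined eligible at the end of this visit, they will then be scheduled for the MRI scan". The schedule table for this group marks task-based fMRI at Visit II only. Under cognitive testing at Visit I it lists only the WTAR reading test.

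**Medical marijuana patients** (same section, Medical Marijuana Participants). At screening, "subjects will be instructed on how to use our phone app for tracking their medical marijuana use, they will fill out some questionnaires", with urine testing and randomisation at the same visit. At baseline, "they will undergo cognitive testing, interviews, questionnaires, and possibly an MRI scan". The schedule places the CANTAB and the first task-based scan at that baseline visit. The optional MRI section adds: "Participants will undergo MRI scanning at baseline and at 1 year after initiation of MM". None of these places describes a session on the scanner tasks before the first scan.

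**The comparison** (II. Specific Aims, Aim 4). Patients are compared with healthy controls: "We will use functional MRI tasks to assess memory, inhibitory control, sustained attention, and risk/reward task performance and brain activation patterns".

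**The analysis** (Analytic Plan, Imaging Data). A linear mixed-effects model is fitted per region or voxel. No term for prior task exposure is named, and the patient-control contrast is not written out.

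**The concern.** Having done a task before can change accuracy, reaction time and the activation the task evokes. If one group meets the task for the first time in the scanner and the other has already worked through it on a computer, a difference between the groups can come from the visit schedule alone. Aim 4 expects patients to show altered task-related activity, so such a difference could be taken as confirmation.

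Analysis cannot repair this. If every control and no patient has the session, exposure and group are the same variable and their effects cannot be estimated separately. The point has to be settled in the design or disclosed in the report.

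A second, smaller issue is that the control session is also the place where the task is tuned. The documents do not say that parameters are fixed before the first scan that enters Aim 4.

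**Working it through.** The plan gives no sample size, power or error rate for Aim 4, so there is no figure to reproduce. The check is a comparison of the two groups' procedures.

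| Item | Healthy controls | Marijuana patients |
|---|---|---|
| Visit before the scan visit | Visit I, outside the scanner | Screening visit |
| Scanner-task session before first scan, per text | Yes, computer testing on the task | None described |
| Same, per schedule table | Not shown | Not shown |
| CANTAB at or before first scan visit | Not listed | Yes, at the baseline visit |
| Task-based fMRI | Visit II | Baseline and 1 year |

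**Step 1: which task is meant.** The text uses the singular and gives no name. The only tasks described for controls are the scanner tasks, so a scanner task is the natural reading. Several paradigms are planned (memory, attention, inhibitory control, risk/reward), and the text does not say whether one or all are run at Visit I.

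**Step 2: whether patients have an equivalent.** Their screening text, baseline text, schedule and MRI section list none. This is an inference from silence in otherwise detailed descriptions; the protocol does not state it outright.

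**Step 3: whether the CANTAB evens things out.** The CANTAB covers attention, working memory and decision-making, but it is not described as the scanner task and controls do not take it. It is a further exposure difference and could act in the opposite direction.

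**Step 4: which results are exposed.** The Aim 4 contrasts on task performance and task activation, most clearly at the first scan. The two descriptions of controls also differ on scan count: the healthy-control procedures show one scan, while the optional MRI section has 25 controls scanned at baseline and after 1 year. If controls are rescanned, both groups will have had an in-scanner exposure by then and the gap may shrink.

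**Step 5: illustration of size.** The 25 controls come from the optional MRI section. The number of scanned patients (25, 50, 75) and the practice shift d in SD units (0.2, 0.3, 0.5) are assumptions; the documents give neither. Take a two-sided 5% two-sample t test with no true group difference. The non-centrality is d × √(n₁n₂/(n₁+n₂)), with n₁ + n₂ − 2 degrees of freedom. For n₂ = 50 and d = 0.3: 0.3 × √(1250/75) = 0.3 × 4.082 = 1.225 on 73 degrees of freedom, and the chance of a significant result is 0.227.

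| Scanned patients (assumed) | d = 0 | d = 0.2 | d = 0.3 | d = 0.5 |
|---|---|---|---|---|
| 25 | 5% | 10.7% | 18.0% | 41.0% |
| 50 | 5% | 12.7% | 22.7% | 52.2% |
| 75 | 5% | 13.8% | 25.1% | 57.3% |

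Any bias of size d would give these figures. They say nothing about whether practice in this trial produces such a shift, and a single t test stands in for models fitted by region or voxel.

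**The case against.** The strongest reply is that the session may not happen as the sentence suggests. The control schedule has no task entry at Visit I, the task is unnamed, and silence about patients does not prove that they are scanned without familiarisation. This stands as a limit on certainty. It does not remove the point, because a reader following the text would run the session for controls only, and the disagreement between text and table itself needs resolving.

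It can also be said that Aim 4 is non-randomised and confounded anyway: controls are free of major illness, medication use and current psychological disorders, while patients seek treatment for pain, sleep or affective symptoms. That is true, and equal exposure would not cure it. Unequal exposure is nonetheless an avoidable addition.

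Three stronger readings are tempting, and the documents do not support them:

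- *All 25 controls and no patients have practised every paradigm.* The singular, unnamed task, the control table and the silence on patients rule out stating this as fact.
- *The listed secondary imaging outcome is compromised.* It is defined as change from baseline to 1 year, which matches the within-patient question of Aim 3; the control Visit I does not touch that change.
- *Early controls were scanned under parameters that later changed.* Nothing says so, and the tuning could be individual calibration.

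**Conclusion.** The point holds as a possible, systematic difference in prior task exposure between the groups in the Aim 4 task-fMRI and task-performance contrasts. It rests on two readings: that the task in the control text is a scanner task, and that patients have no equivalent session. Both are the natural reading, and neither is stated outright.

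The direction and size of any bias, and the paradigms affected, cannot be determined from the documents. The error rates of 11% to 57% depend wholly on assumed shifts and assumed patient numbers and should not be cited as properties of this trial. The randomised comparison, structural MRI and within-patient change under Aim 3 are unaffected, and resting-state connectivity is not directly affected. The remedy is cheap enough that the change should be made despite these uncertainties.

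**What to change.** 1. Reconcile the Visit I text with the healthy-control schedule, and name the task or tasks used there.
2. Make pre-scan task exposure the same in both groups. Either tune the parameters on separate volunteers and drop the session for controls who enter Aim 4, or give scanned patients the same short familiarisation at their existing baseline visit.
3. Fix the task parameters before the first Aim 4 scan.
4. If controls have already been tested, report pre-scan exposure by group, state that the Aim 4 task contrast is confounded by practice, and rest the group claim mainly on structural and resting-state measures.

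Simply excluding every control whose session was used for tuning is not a safe substitute: on the text as written, that could remove the whole control group.

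The cost is a few minutes of patient time, or a few extra volunteers for tuning. If the task turns out not to be a scanner task, or patients do receive an equivalent session, a clarifying sentence would settle the matter.

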Effect of Medical Marijuana on Neurocognition and Escalation of Use

NCT03224468

Date: 1/28/2022

PARTNERS HUMAN RESEARCH COMMITTEE

DETAILED PROTOCOL: Effect of Medical Marijuana on Neurocognition and Escalation of Use

Protocol #: 2015P001600

Principal Investigator: [name].

Co-Investigator: A. [name]

Summary of Changes Made and Rationale

The IRB protocol, attached, was written for a pilot phase of the trial, and was updated when we received the R01. All measures, outcome definitions, and sample size calculations were up to date in clinicaltrials.gov (NCT03224468). The statistical analysis section was amended before any data were analyzed except for the propensity score analysis for missing data, explained below. No changes were made after looking at the data, except for the propensity score analysis.

Method of randomization:

In Year 1 of the study, we realized that many participants, who were interested in obtaining an MMC never obtained one because of barriers such as expense or needing to go outside the usual healthcare system. We therefore changed our randomization from 1:1 to 2:1 MMC:WLC early in the trial in order to have enough participants in the MMC arm.

Outcomes and outcome definitions:

Outcome measures and definitions were updated on 07/19/2017 in clinicaltrials.gov (NCT03224468), but were not explicitly stated in the IRB protocol.

Primary Outcome Measures:

- Cannabis Use Disorder Symptoms (*Time Frame: Baseline to 12 Weeks*)
 - o The DSM-5 Cannabis Use Disorder Checklist will evaluate symptoms of CUD (number of symptoms).
- Changes in Symptoms of Depression and Anxiety (*Time Frame: Baseline to 12 Weeks*)
 - o For those with depression and anxiety symptoms, the Hospital Anxiety and Depression Scale will be used to assess symptoms.
- Changes in Pain (*Time Frame: Baseline to 12 Weeks*)
 - o For those with pain, the Brief Pain Inventory Severity Scale (BPI-S) will be used to assess levels of pain.
- Changes in Sleep (*Time Frame: Baseline to 12 Weeks*)
 - o For those with insomnia, the Athens Insomnia Scale will be used to assess symptoms.

Secondary Outcome Measures

- o General Medical/Psychiatric Health (*Time Frame: Baseline to 12 Weeks*) The Short Form-12 Health Survey (SF-12) will be used to assess self-report of emotional and physical functioning.
- Cognitive Testing (*Time Frame: Baseline to 12 Weeks*)
 - o Verbal learning/memory, attention, working memory, and complex decision-making will be assessed.

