- Brain-based Measures (*Time Frame: Baseline to 1 Year*)

- Changes in resting state functional connectivity and task-associated activation in brain regions involved in reward, inhibitory control, and working memory will be assessed.

The IRB protocol includes exploratory outcomes that were not presented in this manuscript, but will be included in future publications.

Statistical Analysis: The IRB protocol did not include the final statistical plan. When we brought [name], an experienced clinical trial statistician, on this project in Year 2 of the study, well before any analysis had been conducted, he suggested that instead of a random slopes analysis that assumes the effect of the drug will be to gradually increase the effect or outcome, ie a time x treatment interaction, he suggested we should assume a constant treatment effect over the follow up period, 2 weeks, 1 month, 3 months. [name] also advised us not to adjust for covariates as we originally proposed to do, but to only adjust for baseline symptoms, since randomization should have accounted for differences and we had no strong prior information about what covariates would have an important effect on CUD in people seeking cannabis for medical complaints. [name], without access to the data, made these recommendations to Drs [name] and [name] after which [name], who had access to the data, implemented the analyses.

Propensity score analysis for missing data: We could not ensure that participants in the MMC condition obtained an MMJ card, and we could not give participants a MMJ card because of state and hospitals regulations, a stated limitation of the study. Thus, we conducted a post hoc sensitivity analysis to verify the positive findings of the primary analysis in the final stages of the analysis when we realized that there was a problem with differential drop-out between the randomization and the baseline visit in the MMC and WLC groups.

Sample size calculation:

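### Baseline follows randomisation and, in the card arm only, depends on getting a card; the primary analysis set is not named, and the admitted differential loss is met only by an undescribed post hoc analysis.

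*Combined protocol and SAP*

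**What the plan says.** **Randomisation.** Under V. Study Procedures, Medical Marijuana Participants, allocation happens at the screening visit: "Also at this visit, participants will be randomized to either the active study group or the waitlist control group".

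**Route to baseline.** The Study Design text then separates the arms. For MMC, "When participants in the active study group receive their medical marijuana card, they will be scheduled for a baseline assessment". By contrast, "participants in the waitlist control group will be scheduled for the baseline visit approximately 3-4 weeks following the screening visit". All later assessments are counted from that baseline visit.

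**Non-adherence.** An MMC participant with no application progress at six weeks leaves the main schedule: "the participant will be discontinued from the study and a three-month follow-up visit will be scheduled". For WLC participants who start early, the rule is different: "If this group fails to adhere to the waitlist control, they will be kept in the study".

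**Analysis.** The Summary of Changes gives the primary outcomes a time frame of baseline to 12 weeks. Its Statistical Analysis paragraph assumes a constant effect over the 2-week, 1-month and 3-month visits. It records the advice not to use the covariates first proposed, "but to only adjust for baseline symptoms, since randomization should have accounted for differences". It adds a second reason: little was known beforehand about which covariates matter for cannabis use disorder (CUD) in this population.

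**Known loss.** The Method of randomization paragraph says that "many participants, who were interested in obtaining an MMC never obtained one because of barriers such as expense", and gives this as the reason for moving from 1:1 to 2:1 allocation. The Propensity score paragraph reports that "there was a problem with differential drop-out between the randomization and the baseline visit in the MMC and WLC groups", found in the final stages of analysis and addressed by a post hoc sensitivity analysis.

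No section names an intention-to-treat, modified or per-protocol set, or says whether randomised participants without a Visit 2 enter the primary analysis.

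**The concern.** Randomisation makes the arms comparable at Visit 1. If the analysis starts at Visit 2, the MMC arm has by then been filtered by whether a card was obtained, and the WLC arm has passed no such filter. The estimate may then mix the effect of assignment to a card with differences between people who obtain cards and people who do not.

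All four primary outcomes share this structure, so all four are exposed. The barriers the sponsor names are expense and having to go outside usual care. These could plausibly relate to mood, pain, sleep or substance use, though the documents give no evidence either way. WLC loss before baseline is also possible and is not quantified.

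The first reason given for leaving covariates out appeals to randomisation. That argument covers everyone randomised; it does not carry over to a subset selected afterwards in one arm.

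**Working it through.** **1. The two routes side by side**

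| | MMC | WLC |
|---|---|---|
| Randomised | Visit 1 | Visit 1 |
| Baseline triggered by | card receipt | calendar, 3-4 weeks |
| If the assigned course is not followed | discontinued at six weeks if no progress, with one three-month visit | kept in the study |
| Clock for later visits | card-triggered baseline | calendar baseline |

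An MMC participant who makes progress but never receives a card meets neither the card trigger nor the six-week rule. The documents describe no outcome visit for that person.

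**2. Time since randomisation**

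Take one month as 4 weeks, and three months as 12 weeks (outcome definitions) to 13 weeks (diary payment schedule).
- WLC: 3-4 plus 2, 4 and 12-13 gives weeks 5-6, 7-8 and 15-17.
- MMC: card receipt plus 2, 4 and 12-13 weeks, with no stated upper limit on time to card for those making progress.
- Discontinued MMC: week 12-13 if the three-month visit is timed from Visit 1, or 6 + 12-13 = 18-19 if timed from discontinuation. The text does not say which.

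**3. Illustrative size of the bias**

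The documents give no loss rates, so every input here is an assumption.
- q, the fraction of MMC not reaching baseline: 0.2-0.5.
- delta, the difference between obtainers and non-obtainers, equal at baseline and follow-up: 0.2-0.5 SD.
- r, the correlation of baseline with follow-up: 0.5-0.7.
- No true effect, and no selective loss in WLC.

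Obtainers then differ from the full randomised arm by q x delta at both times. Adjusting for baseline removes the share r, so

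residual bias = q x delta x (1 - r).

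- Low: 0.2 x 0.2 x 0.3 = 0.012 SD.
- Middle: 0.35 x 0.35 x 0.4 = 0.049 SD.
- High: 0.5 x 0.5 x 0.5 = 0.125 SD.

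A simulation with 1.5 million per arm and no true effect gives about 0.012 at the low end and about 0.12 at the high end.

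**4. Scale**

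The Sample size calculation gives 84% power for pain and for depression and anxiety, and 90% for insomnia, with about 33 per group, two-sided 0.05. Solving the noncentral t distribution for the standardised difference gives d = 0.738 (84%) and d = 0.810 (90%).
- 0.012/0.738 = 1.6%; 0.049/0.738 = 6.6%; 0.125/0.738 = 16.9%.
- 0.012/0.810 = 1.5%; 0.125/0.810 = 15.4%.

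No such ratio is given for CUD symptoms, because the plan states means of 0.4 and 0.1 without an SD.

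**5. Whether Visit 1 data can serve**

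The measures table marks the DSM-5 CUD checklist, BPI, AIS and HADS at the screening visit. Every randomised participant should therefore have an early value on each primary scale. The text does not say whether these were completed before allocation was known, and this should be confirmed.

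**The case against.** **The problem is disclosed and partly handled.** The sponsor reports the differential drop-out, calls the inability to ensure cards a limitation, and ran a propensity-score analysis. That analysis may resemble the weighting proposed below. This stands in part. What remains is that it is post hoc, serves only as a sensitivity analysis, and is given without target population, covariates or weights. The change to 2:1 restores MMC numbers but does not undo selection.

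**The selection is inferred.** No sentence says that participants without a Visit 2 were left out. This stands, and is why the claim is worded as what the comparison appears to be. The link between the named barriers and prognosis is likewise plausible but undocumented.

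**Counting from baseline is a legitimate choice.** It aligns MMC participants by time since card. This also stands: it answers a different question, which is a reason to report both contrasts and not to replace one with the other.

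**Stronger readings that a reader might infer, and that the documents do not support:**
- That the primary result is shown to be biased, or biased towards the positive findings. Neither loss rates nor the direction of any prognostic difference is given.
- That the case for leaving out covariates collapses. Only one of its two reasons depends on intact randomisation.
- That a common 15-17 week window would put the arms on one clock. The discontinued participants' visit falls at 12-13 or 18-19 weeks, outside it on either reading, and a participant with a card at week 6 would have the three-month visit at week 18-19.
- That a definite loss of power follows. Any such figure needs an assumed card uptake and a total of 200, whereas the Screening text plans 200 per group and VI. Participant Enrollment gives 400.

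**Conclusion.** The concern holds in a limited form and should be fixed. The arm-specific route to baseline, the unequal handling of non-adherence, the missing analysis set and the conceded differential drop-out are all on the page. Taken as written, a baseline-anchored analysis adjusted only for baseline symptoms compares a card-selected MMC subset with WLC, and that is not a purely randomised comparison.

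The size and direction of any bias are unknown. The 0.012-0.125 SD range, about 2-17% of the back-solved d = 0.738, illustrates the assumptions listed and does not estimate anything for this trial. The bias is zero if obtainers and non-obtainers have the same prognosis; selective WLC loss would add a term of either sign. Confidence is medium, because one sentence stating that everyone randomised was analysed would settle the main question.

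**What to change.** 1. State the primary analysis set. Report loss between Visit 1 and Visit 2 in each arm, with reasons.
2. Alongside the current contrast, report an as-randomised estimate in all participants randomised at Visit 1, with the Visit 1 CUD checklist, BPI, AIS and HADS as covariates.
3. Include the three-month visit of discontinued MMC participants in that estimate, and state its time origin and instruments. Report time since Visit 1 for outcome assessments in both arms, without forcing a single narrow window.
4. Handle the remaining missing outcomes by inverse-probability weighting or multiple imputation from Visit 1 variables, with sensitivity analyses for departures from missing at random.
5. Specify the existing propensity-score analysis: target population, covariates and weights.
6. If the contrast among baseline attenders stays the main result, do not present it as purely randomised. Label the added analyses as decided after data were seen.

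**Cost.** No new visits or instruments, and no change to how participants are managed. The modelling is heavier. The as-randomised estimate is the effect of assignment, so it is diluted relative to the effect of holding a card. For MMC participants with no planned outcome visit, the result rests on assumptions that the data cannot test.
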